**Table 3-1: TTI-621 Dose Levels by Cohort**

Cohort	N	Dose (once weekly)
0	3 (+ 3)	0.01 mg/kg
1	3 (+ 3)	0.05 mg/kg
2	3 (+ 3)	0.1 mg/kg
3	3 (+ 3)	0.3 mg/kg
4	3 (+ 3)	1 mg/kg
5	3 (+ 3)	3 mg/kg
6	3 (+ 3)	10 mg/kg

Subjects will receive TTI-621 at the assigned dose once weekly for a planned 3 weeks of treatment/observation for DLT assessment. In the absence of DLT (as defined in [Section 3.2.2](#)) in 3 evaluable subjects within a cohort, dose advancement will proceed through the successive cohorts. All subjects in each dose cohort must have completed the DLT observation period before the next dose cohort commences treatment.

Subjects will be considered evaluable for DLT if they received all 3 weekly doses within the specified treatment/observation period or if they experienced an AE meeting the criteria for DLT during that time. Those who drop out of the study during the first 3 weeks for reasons other than toxicity or who experience a delay in dosing of more than 3 days for reasons other than DLT are considered unevaluable for DLT and will be replaced with a new subject enrollment. For subjects who experienced a treatment delay, the DLT observation period will extend 7 days beyond the third dose of TTI-621.

If DLT as defined below is encountered in 1 subject within a particular dose cohort, additional subjects will be treated in that cohort as outlined in [Table 3-2](#). Based on the incidence of DLT, the MTD will be determined. Depending upon the tolerance at a particular dose level, intermediate dose levels may be studied to more closely characterize DLT and more accurately identify the MTD as recommended by the Safety Review Committee (SRC).

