### 3.3.2 Phase 1b Dose Optimization Part 4 (to be enrolled as of Amendment 9)

A minimum of 3 patients will be treated in each cohort sequentially in a 3 + 3 design. The planned dose escalation levels are shown in [Table 3-4](#). Patients will receive once weekly dosing of TTI-621 at the dose levels in their assigned cohort regimen (Week 1 given on Day 1, Week 2 given on Day 8, and Week 3 given on Day 15). The DLT observation period is 21 days. Patients will be considered evaluable for DLT if they receive all 3 weekly doses within the DLT evaluation period or if they experience an AE meeting DLT criteria during that time. If a patient experiences a non-DLT event that requires a dose to be held per dose modification guideline ([Section 6.5](#)), the DLT evaluation period can be extended to 28 days. If a DLT occurs in 1 of 3 patients within a cohort, 3 additional patients will be treated at that cohort regimen. In the absence of DLT, enrollment will proceed sequentially through the planned dose levels.

Alternative dose escalation including evaluation of intermediate doses, expansion of an existing dose level, evaluation of alternative regimens/schedules including a dose ramp-up design following different dose intensification increments and schedule, and modification of dosing frequency and/or IV infusion rate are all permissible if supported by the evolving data and a SRC decision. All patients in each cohort must have completed the 21-day DLT period before the next cohort begins treatment. The MTD of TTI-621 will be the dose below the one in which  $\geq 2$  DLTs are observed among 6 treated patients.

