### **6.5.2 Criteria for Retreatment and Dose Delays**

TTI-621 is given as weekly infusions. Before each TTI-621 dose can be delivered, the patients' ANC must be  $\geq 1 \times 10^9/L$  and the platelet count must be  $\geq 75 \times 10^9/L$  or baseline. In addition, all other toxicity considered to be related to treatment with TTI-621 must have resolved to  $\leq$ Grade 1 or to the patient's baseline values with the exceptions listed below. If other AEs, not listed below, resolve to a level that is determined to be acceptable (and  $\leq$ Grade 2) for TTI-621, re-dosing is allowed based on a benefit-risk assessment by the investigator and medical monitor on a case by case basis. The decision will be documented.

Exceptions:

- Grade 2 gastrointestinal symptoms such as nausea, vomiting, and diarrhea that are easily treatable
- Grade 2 fatigue or other constitutional symptoms
- Grade 2 lymphopenia, neutropenia, and/or leukopenia in the absence of opportunistic infection
- Grade 2 thrombocytopenia in the absence of clinically meaningful bleeding
- Grade 2 anemia in the absence of shortness of breath and/or congestive heart failure
- Transient asymptomatic  $\leq$ Grade 3 laboratory abnormalities that is manageable with standard supportive care and considered not clinically significant following agreement between investigators and the sponsor or designees.

If the patient fails to meet the above-cited criteria for retreatment, initiation of the next dose of TTI-621 should be delayed for 1 week. At the end of that time, the patient should be re-evaluated to determine whether the criteria for retreatment have been met. If toxicity does not resolve by three weeks then the patient will be considered for removal from the study. If, in the opinion of the investigator and the medical monitor, it is in the patients' best interest to continue treatment with TTI-621 then the dose of TTI-621 should be reduced by at least 1 dose level after recovery of the toxicity or toxicities in question. In such circumstances, when a dose reduction of TTI-621 is required, no re-escalation of dose will be permitted.

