#### 6.6 Intra-patient Dose Reduction and Escalation (Phase 1b Dose Optimization Part 4: DLT evaluation period)

Intra-patient dose reductions of TTI-621 are not permitted in the DLT evaluation period (Week 1-3) in the phase 1b dose optimization unless the patient experiences a DLT attributed to TTI-621. If a patient experiences a DLT during the first 21 days, treatment should be held and the event counted toward the assessment of MTD for the given cohort. These patients may continue in the study upon resolution of the toxicity at a reduced dose

level. Patients who receive a reduced dose of TTI-621 during the DLT evaluation period for reasons other than DLT will be replaced.

During phase 1b dose optimization, when the MTD or recommended phase 2 dose of TTI-621 is determined, all patients who have received TTI-621 at a dose lower than the recommended dose for a minimum of 4 weeks may dose escalate to the recommended dose in the absence of PD or unacceptable treatment-related toxicity at the investigator's discretion and with the medical monitor's approval. Patients for whom an increase in the dose of TTI-621 is being considered must have TEAEs resolve to  $\leq$ Grade 1 or baseline or to a level that is acceptable to the investigator (non-hematologic toxicity must be  $\leq$ Grade 2, hematologic toxicities must be recovered to levels above the minimum requirement for TTI-621 dosing).

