## **1 Introduction**

The purpose of this Statistical Analysis Plan (SAP) is to describe in detail the statistical summaries to be performed by Sarah Cannon Development Innovations for Pfizer study *TTI-621-01, A Phase 1a/1b Dose Escalation and Expansion Trial of TTI-621, a Novel Biologic Targeting CD47, in Subjects with Relapsed or Refractory Hematologic Malignancies and Selected Solid Tumors*. The scope of this document includes statistical analyses to be prepared for the abbreviated Clinical Study Report (aCSR).

This SAP is based on version 9.0 of Clinical Protocol TTI-621-01 (dated 20 Feb 2019) and version 14.0 of Case Report Form (CRF) TTI-621-01 (dated 17 Apr 2020). If amendments are made to either of these documents, this SAP will be updated as appropriate.

Statistical analyses to be performed by Pfizer Inc. or by vendors other than Sarah Cannon Development Innovations are outside of the current scope of this document. In particular, it is currently planned that analyses of pharmacokinetic/pharmacodynamic (PK/PDx) data will take place outside of Sarah Cannon Development Innovations; the text of the SAP describing these analyses has been provided as-is to Sarah Cannon Development Innovations for inclusion in the SAP.

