### **1.1.3 Phase 1b Dose Optimization (Part 4)**

The primary objective of the dose optimization phase is to further evaluate the safety and tolerability of TTI-621 at dose levels higher than the initially recommended Phase 1b dose of 0.2 mg/kg (as determined during Phase 1a dose escalation) and the MTD will be re-assessed per revised DLT criteria following a 3+3 dose escalation schema. The DLT criteria are revised based on the totality of safety data collected thus far from the Phase 1a and 1b dose expansion phase of the study. The starting dose for this further dose evaluation will be the highest dose of TTI-621 evaluated (0.5 mg/kg) during Phase 1b dose expansion following dose intensification regimens permissible per protocol (Part 2 and Part 3).

Primary endpoints are:

- Dose Limiting Toxicities (DLTs) at escalated doses of TTI-621
- Incidence and severity of AEs

A DLT is defined in Phase 1b Dose Optimization (Part 4) as any of the following TEAEs that occur during the DLT period and that are considered at least possibly related to study treatment by the investigator. Note that any AEs for which the relationship to study treatment cannot be ruled out should be considered possibly related:

- Grade 4 thrombocytopenia ( $<25 \times 10^9/L$ ) lasting  $>72$  hours or a platelet count  $\leq 10 \times 10^9/L$  at any time
- $\geq$  Grade 3 thrombocytopenia with bleeding (except epistaxis or gingival bleeding that is less than 24 hours in duration and does not require medical intervention, or normal menses) or requiring platelet transfusions
- Grade 4 anemia, unexplained by underlying disease
- Grade 4 neutropenia lasting  $>72$  hours
- Grade 3 febrile neutropenia lasting  $>72$  hours
- Grade 4 febrile neutropenia
- Grade 3 or higher non-hematologic toxicity with the following exceptions:
  - Grade 3 nausea and/or vomiting lasting  $<72$  hours with standard supportive care
  - Transient Grade 3 fatigue lasting  $\leq 72$  hours
  - Transient asymptomatic Grade 3 laboratory abnormalities considered not clinically significant following agreement between investigators and the sponsor's medical monitor and that last  $<72$  hours with standard supportive care
- Other  $\geq$  Grade 2 TTI-621-related non-hematologic toxicities that, in the opinion of the investigator, require a dose reduction or discontinuation of TTI-621

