### DLT-evaluable set (for Part 1 and non-Q2W Part 4 only)

The DLT-evaluable set consists of 1) subjects who have received all 3 doses within the DLT evaluation period, OR 2) subjects who experienced an adverse event (AE) meeting DLT criteria during that time. Those who drop out of the study during the DLT evaluation period for reasons other than toxicity or who experience a delay in dosing of more than 3 days for reasons other than DLT are considered unevaluable for DLT.

The DLT evaluation period consists of the first 21 days on study for subjects initially assigned to Part 1 and non-Q2W Part 4. For subjects who experienced a treatment delay, the DLT observation period will extend 7 days beyond the third dose of TTI-621.

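### SAP section 2 applies the Part 1 three-day delay exclusion to weekly Part 4, where Protocol 3.3.2 has no such limit; separately, the DLT summary falls on all dosed subjects, not on the DLT-evaluable set

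*SAP*

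**What the plan says.** **Evaluability.** The SAP states its basis: "This SAP is based on version 9.0 of Clinical Protocol TTI-621-01". Its section 2 defines one DLT-evaluable set for Part 1 and non-Q2W Part 4: subjects with all three doses in the period, or with a DLT. Subjects "who experience a delay in dosing of more than 3 days for reasons other than DLT are considered unevaluable for DLT". For delayed subjects it runs observation to seven days after the third dose.

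In the protocol the three-day exclusion stands in section 3.2.1, which covers Phase 1a; there, such subjects "are considered unevaluable for DLT and will be replaced with a new subject enrollment". Part 4 has its own rule in section 3.3.2: "Patients will be considered evaluable for DLT if they receive all 3 weekly doses within the DLT evaluation period", or if they have a DLT. After a hold for a non-DLT event, "the DLT evaluation period can be extended to 28 days". Section 6.5.2 sets the length of a hold: when retreatment criteria are not met, "initiation of the next dose of TTI-621 should be delayed for 1 week". Section 6.6 adds: "Patients who receive a reduced dose of TTI-621 during the DLT evaluation period for reasons other than DLT will be replaced".

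**Population for the DLT summary.** SAP 1.1.3 lists "Dose Limiting Toxicities (DLTs) at escalated doses of TTI-621" as a primary endpoint of Part 4, and SAP 1.1.1 does the same for Part 1. Among the planned analyses, the DLT-evaluable set is named only in the disposition list (SAP 3.1). The DLT summary is in SAP 3.5.1, under section 3.5, whose stated population is the Safety Analysis Set (at least one dose). SAP 1.2.5 requires six DLT-evaluable subjects at the MTD or recommended dose. Protocol 8.4.4 promises an exact 95% interval for the DLT rate in the escalation phase; SAP section 3 says only that selected tables may carry Clopper-Pearson intervals.

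**The concern.** There are two separate points. Both concern how DLTs are reported, not how escalation decisions are made.

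1. A rule written for Part 1 has been applied to Part 4, where the protocol has a different one. It removes from the set the patients whom the 28-day extension allows to be kept.
2. A primary endpoint is summarised on a wider denominator than the one the MTD rests on. Dosed but unevaluable subjects did not complete DLT observation, so counting them lowers the DLT percentage.

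The points interact. Point 1 does not touch the DLT rate while the set is used only for disposition. If point 2 were corrected alone, the Part 1 exclusion would move into the Part 4 DLT table.

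**Working it through.** **The plan's own DLT figures.** No stated number is in dispute. The nearest is the SAP 1.2.2 table of 3+3 escalation probabilities, which assumes denominators of 3 and 6. With true DLT rate p, P(escalate) = (1−p)³ + 3p(1−p)²·(1−p)³.

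- p = 10%: 0.729 + 0.3 × 0.590 = 0.906 (stated 0.91)
- p = 30%: 0.343 + 0.9 × 0.168 = 0.494 (stated 0.49)

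All eight stated values reproduce after rounding.

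**Point 1: timing.** Protocol 3.3.2 puts the doses on Days 1, 8 and 15. A delay of d days before the third dose moves it to Day 15 + d.

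| Delay (days) | Third dose | Protocol 3.3.2, extended to 28 days | SAP section 2 |
|---|---|---|---|
| 0–3 | Day 15–18 | evaluable | evaluable |
| 7 | Day 22 | evaluable | unevaluable |
| 14 | Day 29 | unevaluable | unevaluable |

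The conflict is the one-week hold. If the period is not extended, Day 22 is outside 21 days, and both documents drop the patient. The SAP's own extension, to seven days after dose 3, does not change the middle row: it lengthens observation but does not cancel the exclusion. A delay of 4 days (dose 3 on Day 19) would also split the documents, but Protocol section 7 treats a visit more than 2 days off plan as missed. The conflict therefore arises mainly with holds for adverse events.

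**Point 2: denominators.** Protocol 1.7 reports that Cohort 2a had 7 enrolled, 6 DLT-evaluable and 1 DLT. The Clopper-Pearson 95% limits for x out of n are the 2.5% quantile of Beta(x, n−x+1) and the 97.5% quantile of Beta(x+1, n−x).

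- DLT-evaluable set: 1/6 = 16.7% (0.4% to 64.1%)
- Safety Analysis Set: 1/7 = 14.3% (0.4% to 57.9%)

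The second line assumes that all seven were dosed. That fits the 179 subjects enrolled (Protocol 1.7) and the Safety Analysis Set of 179 (Protocol Table 1-1).

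**The points together (illustration only; the documents report no such case).** Take a Part 4 level with 6 protocol-evaluable patients, 1 DLT, and one DLT-free patient with a one-week hold under the extended period. If the SAP set as now defined became the denominator, the rate would be 1/5 = 20.0% (0.5% to 71.6%) instead of 1/6 = 16.7% (0.4% to 64.1%). The set would also hold five subjects, not the required six.

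**The case against.** - **Point 1 has no present consequence.** It changes a disposition count, depends on an extension that is optional, and has no reported case. All true. It remains a stated rule that differs, without a reason given, from the protocol version the SAP names.
- **The operative rule may be recorded elsewhere.** The SAP's change history mentions notes-to-file. SAP 1.2.5 describes a 2.0 mg/kg cohort and a biweekly expansion that Protocol Table 3-4 does not contain, so Part 4 had moved on. Such a note could justify the rule, but the SAP cites none for it.
- **Point 2 follows the protocol's default.** Protocol 8.4.4 uses the Safety Analysis Set unless otherwise specified and names no DLT denominator, and Protocol 8.2 defines no DLT-evaluable set. This stands: the denominator is a gap within the SAP, not a breach of the protocol.
- **The denominator is inferred.** No sentence in the SAP says that the DLT table uses all dosed subjects; it follows from the population stated for section 3.5. The table list is a separate document (SAP section 5) and was not available. The inference is nonetheless the direct reading.
- **The numbers barely move.** Correct. Any subject with a DLT is evaluable, so no DLT leaves the numerator, and all DLTs are listed.
- **The interval.** The SAP permits exact intervals and covers an abbreviated report. Permission is still weaker than the protocol's commitment, although that commitment is for the escalation phase only.

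**Conclusion.** Both points hold, and both are minor. The SAP's Part 4 evaluability rule conflicts with Protocol 3.3.2 for a DLT-free patient with a one-week hold when the period is extended; at present this affects a disposition count only. The DLT summary is placed on all dosed subjects, which in Cohort 2a gives 14.3% instead of 16.7%, a difference that is small beside either interval. The protocol's exact 95% interval for the escalation-phase DLT rate is no longer assured. No escalation decision changes and no DLT is lost. The conclusion assumes that all seven Cohort 2a subjects were dosed, and that no note-to-file or table specification outside the two documents sets a different rule.

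**What to change.** Make both edits together.

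1. **SAP section 2.** Give Part 1 and weekly Part 4 separate evaluability definitions. Reconcile the Part 4 definition with Protocol 3.3.2, including the possible 28-day extension, or state why it departs and cite the note-to-file if there is one. Also say how patients replaced under Protocol 6.6 are handled. Protocol 3.3.2 is silent on them too, so this is a point to settle, not a SAP departure.
2. **SAP 3.5.1.** Report the DLT rate per dose level on the DLT-evaluable set with an exact 95% interval. The protocol commits to that interval for the escalation phase; doing the same in Part 4 is a recommendation. Show DLTs in all dosed subjects as supportive.

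The cost is SAP wording and one table denominator, with no new data. Check the separate table list for the same denominator.

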### Full Analysis Set

The Full Analysis Set is the primary population for all analyses of efficacy-related data. The Full Analysis Set is identical to the safety analysis set, which includes all subjects who received at least 1 dose of study treatment.

### Response-Evaluable Set (for Part 3 only)

The Response-Evaluable Set will serve as a secondary population for the analysis of overall response for Part 3. The Response-Evaluable Set is a subset of the Full Analysis Set, with subjects excluded if they withdraw from the study without post-baseline assessment of overall response for a reason other than early progression or safety.

### PK-evaluable Set

The Pharmacokinetic (PK)-evaluable Set consists of treated subjects with adequate blood sampling to estimate at least 1 pharmacokinetic PK parameter.

Immunogenicity-evaluable Set

The immunogenicity analysis population includes all treated subjects with at least 1 ADA sample (pre-dose or post-treatment) analyzed. If a subject only has pre-dose baseline data and no post-treatment immunogenicity data, this subject is not evaluable for subject-level ADA and NAb status and should not be included in subject-level data analysis (eg. overall ADA/NAb incidence, duration of ADA/NAb response).

### **3 Analyses and Summaries**

The statistical analyses performed for this study will be summarized by the following unless indicated otherwise:

- Initial assigned dose levels or initial assigned dosing schedules (in the case of Part 4 biweekly) for Part 1 and Part 4 (Dose Escalation cohorts)
- Monotherapy or combination therapy for Part 2 and Part 3
- Indication within monotherapy and by combination therapy for Part 2 and Part 3

The statistical analyses will be performed using SAS® version 9.2 or later (SAS Institute Inc., Cary NC). Programming specifications will be prepared which describe the datasets and variables created for this study. The datasets will be prepared using the most recent version of the Clinical Data Interchange Standards Consortium (CDISC) Study Data Tabulation Model (SDTM) and Analysis Dataset Model (ADaM). The source SDTM and ADaM datasets from which a statistical analysis is performed (including interim safety reviews) will be archived with the Sponsor.

The following data conventions will be employed in the study.

- Summary tables for continuous variables will contain the following statistics: N (number in population); n (number with data); mean; standard deviation; median; minimum; and maximum. Selected tables also may include 2-sided 95% confidence intervals (CIs) on the mean, calculated using a t-distribution approximation.
- Summary tables for categorical variables will include: N (number in denominator); n (number in numerator); and percent. Selected tables also may include 2-sided 95% CIs for the percent, calculated using the Clopper-Pearson method.
- Data from all study centers will be pooled for all analyses.
- The baseline value for a given parameter is the last value prior to the time of the first dose. A value is considered to be post-baseline if it is obtained after the time of the first dose.
- Study Day is defined as Calendar Date – Date of First Treatment + 1 if the calendar date is on or after the date of the first treatment, and Calendar Date – Date of First Treatment if the calendar date is before the date of the first treatment.
- Partial dates will be displayed as partial dates in listings and missing dates will be displayed as missing. The corresponding Study Day for partial or missing dates will be displayed as missing in listings.
- Unless specifically noted later in this SAP, missing data will not be imputed.

### **3.1 Subject Disposition**

The number of subjects in each of the following subsets will be presented by cohort and overall.

- Safety Analysis Set
- DLT Evaluable Analysis Set (for Part 1 and non-Q2W Part 4 only)
- Full Analysis Set
- Response-Evaluabe Set (for Part 3 only)
- PK-Evaluabe Set
- Immunogenicity-evaluabe Set

The number and percentage of subjects will be calculated based on the full analysis set as applicable:

- Discontinued study treatment (overall and by reason, for each drug)
- Discontinued study (overall and by reason)
- Follow-up status

The duration of study participation (defined as Date of study discontinuation – date of first dose + 1) will be summarized for subjects in the Safety Analysis Set.

All disposition data will be presented in a listing, with a flag for treatment discontinuation and a flag for study discontinuation related to COVID-19.

